C.7. Plasmin and its pro-inflammatory effects: Tranexamic acid is a lysine analogue that interferes with binding of plasminogen to fibrin, which is required for plasmin activation.⁴² Plasmin has pro-inflammatory effects by activating monocytes, neutrophils, platelets, endothelial and dendritic cells and induces pro-inflammatory genes.^{51,52} Plasmin also induces chemotaxis of monocytes and dendritic cells and in-vitro and in-vivo studies have demonstrated the ability of plasmin to stimulate the production reactive oxygen species and promote the release of lipid mediators and cytokines via complement activation.^{51,53} Tranexamic acid benefits in cardiac surgery have been hypothesized to be secondary to a reduction in the inflammatory response, possibly via a reduction of plasmin activation.⁵³⁻⁵⁵ The mortality benefit associated with tranexamic acid may occur secondary to an anti-inflammatory effect due to a reduction in plasmin activation. (Fig 4.)

C.8. Safety and dosing of tranexamic acid: Tranexamic acid has been most commonly used in cardiac surgery and orthopedic surgery for its blood transfusion reduction effects with the risks of thrombotic complications and post-operative seizures being the most common complications reported with its use.^{49,50,56,57} It has been retrospectively compared to other anti-fibrinolytics used in cardiac surgery and shown to have a similar or better safety profile in most studies. Post-operative seizures, due to a GABA receptor antagonist effect, have also been documented following cardiac surgery and this complication is thought to be a dose dependent effect.^{58,59} An orthopedic meta-analysis demonstrated no higher risk of venous thromboembolism following hip and knee replacement, surgeries typically thought to be at increased risk of thromboembolism.⁴⁹ The literature does suggest that further higher level studies are

[figure not shown]

Fig 4. Pro-inflammatory and coagulation system effects of plasmin. Levy JH. *Lancet*. 2010 Jul 3;376(9734):3-4

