required to verify the safety profile of lysine analogue anti-fibrinolytics in the non-injured patient population.^{49,60} The CRASH-2 trial, which looked at over 20,000 patients demonstrated no differences in deaths from vascular occlusive events including myocardial infarction, stroke, and pulmonary embolism and concluded the tranexamic acid safely reduced the risk of death in bleeding trauma patients.⁴¹ Importantly, the trial demonstrated that mortality due to bleeding was increased in patients who received tranexamic acid beyond 3 hours from injury.⁴³ In the retrospective military study (MATTERs, 896 patients) an increased incidence of deep vein thrombosis and pulmonary thromboembolism was demonstrated. These results were, however, confounded by higher injury severity in the tranexamic acid group.⁴⁶

The dosages used in the trauma population studies have been 1 to 2 grams either in loading and/or infusion route, all within the first 8 hours from injury. For the CRASH-2 trial, the dosage regimen was selected to provide a fixed dose within the range shown to inhibit fibrinolysis in larger patients and safe in smaller patients (10 mg/kg loading and 1mg/kg/hr infusion dose).⁴¹ For the military MATTERs study, 1 gram of tranexamic acid was given as a loading dose with the potential for repeat loading dosages.⁴⁶ Based upon these prior studies, the most safe and optimal dosing regimen in trauma patients at risk for bleeding remains obscure.⁶⁰

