Further and in relation to interim safety analysis, safety data by study groups labeled as Interventional group (Early using of tranexamic acid) and Control group (Standard of care) will be provided periodically to DSMB. These processed data will provide information on safety outcomes by treatment group, ascertain the consistency between results for primary and secondary outcomes, and inspect the consistency of treatment effects across subgroups. Safety data of the study include serious adverse events regarding frequency, anticipated or unanticipated, individual description for each event and dates. Other data will be provided as well as any additional safety analysis upon DSMB request. Mortality will be reported as an overall in our periodic reports (every 6-9 months depends on accrual rate) to DSMB however we will report mortality individually as treatment A and B at each of the trial two formal interim analyses. Data will be summarized in tables (3-6)

Table 3 Possible Adverse effects

	Center1		Center2		Center3		Center4		Center5		Total	
	A	B	A	B	A	B	A	B	A	B	A	B
Patients numbers												
Transfusion related lung injury n, (%)												
Allergic/anaphylactic reaction												
Circulatory overload												
Infection												
Febrile reaction												
Hemolytic reaction												
!!!												
!!!												
!!!!												

Table 4 Unexpected Adverse Effects

	Center1		Center2		Center3		Center4		Center5		Total	
	A	B	A	B	A	B	A	B	A	B	A	B
Patients numbers												
1. n,(%)												
2.												
3.												
4.												

Table 5 Primary outcomes for patients in the Study

	Center1		Center2		Center3		Center4		Center5		Total	
	A	B	A	B	A	B	A	B	A	B	A	B
Number of Patients												
24 hr Mortality n, (%)												
30 day Mortality n, (%)												

Table 6 Secondary outcomes for patients in the Study

	Center1	Center2	Center3	Center4	Center5	Total
--	---------	---------	---------	---------	---------	-------

	A	B	A	B	A	B	A	B	A	B	A	B
Number of Patients												
Hyperfibrinolysis												
Acute lung injury (%)												
Multiple organ failure (%)												
Nosocomial infection (%)												
Improved shock parameters (%)												
Early resuscitation need (%)												
Transfusion requirements (%)												
Early seizures (%)												
Pulmonary embolism (%)												
Reduce or prevent the early coagulopathy as demonstrated by improving presenting INR (%)												

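### The DSMB adverse-effects table has no thrombotic row, so deep vein thrombosis, myocardial infarction and stroke have no pre-specified by-arm count

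*Combined protocol and SAP*

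**What the plan says.** Section 4 of Appendix 4 sets out the tables that go to the DSMB, with columns A and B for each centre and in total. "Table 3 Possible Adverse effects" has six named rows: "Transfusion related lung injury n", "Allergic/anaphylactic reaction", "Circulatory overload", infection, "Febrile reaction" and "Hemolytic reaction". Three unlabelled filler rows follow. Table 4 (unexpected effects) has blank rows, Table 5 covers mortality, and Table 6 covers secondary outcomes, including early seizures and pulmonary embolism.

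Protocol section C.8 describes the drug's known hazards in other terms. From surgical use it reports the "risks of thrombotic complications and post-operative seizures being the most common complications reported with its use". Of the retrospective military study it says "an increased incidence of deep vein thrombosis and pulmonary thromboembolism was demonstrated", and then adds that higher injury severity in the treated group confounded that result.

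The DSMB charter (Appendix 3, Safety Analyses) makes mortality the primary safety endpoint and lists nine further items to monitor. Early seizures and in-hospital pulmonary embolism are items 4 and 5. Items 7 to 9 are the general categories of adverse events, unexpected events and expected events.

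**The concern.** A by-arm table of possible adverse effects should carry the events that the protocol itself regards as hazards of the study drug. This one is built mostly around reactions to blood products and has no row for a clot of any kind.

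The charter leaves safety stopping to clinical judgement, with no numerical limit for any adverse event. What the DSMB can judge therefore depends on what is set before it by arm. Thrombotic events that are not named in advance may be scattered among free-text adverse events, labelled differently by site, and never added into one count per arm. A modest imbalance is easily overlooked in that form. The trial enrols under exception from consent for emergency research, which makes clear reporting of known risks more important.

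**Working it through.** No sample size, power or alpha figure underlies this point, so the check is a reading of the lists against each other.

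**Step 1: classify the six named rows of Table 3.**
- Transfusion-type: lung injury related to transfusion, circulatory overload, febrile reaction, hemolytic reaction (4 of 6).
- Not exclusive to transfusion: allergic/anaphylactic reaction, which section P.5 also treats as a possible reaction to study product, and infection, which overlaps a secondary outcome (2 of 6).
- Thrombotic events or seizures: 0 of 6.

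**Step 2: trace each hazard mentioned in C.8 through the plan.**

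| Event | Defined in I.4 | Named as expected event in I.4.10 | Named on charter list | Row in Table 3 | By-arm row in Tables 4 to 6 |
|---|---|---|---|---|---|
| Seizure | Yes (I.4.5) | Yes | Yes (item 4) | No | Yes (Table 6) |
| Pulmonary embolism | Yes (I.4.6) | No | Yes (item 5) | No | Yes (Table 6) |
| DVT | No | No | No | No | No |
| Myocardial infarction | No | No | No | No | No |
| Stroke | No | Yes | No | No | No |

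Seizure and pulmonary embolism are covered. For DVT, myocardial infarction and stroke, the number with a named by-arm row is 0 of 3, and the number named on the charter list is 0 of 3. DVT and myocardial infarction appear only in the background section.

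**Step 3: follow a DVT through the general adverse-event route.** I.4.8 makes an event reportable if it is unexpected, serious, and related or possibly related to the intervention. I.4.10 treats a broad class of major complications common after injury as expected, to be recorded from the discharge summary. A post-injury DVT can reasonably be placed in that class. If it is, it fails the unexpected test in I.4.8 and does not belong in Table 4. Table 3 has no row for it, so no named by-arm count results. It would still fall under charter item 9 (expected events), but without a line of its own. Stroke, which I.4.10 names as expected, follows the same path.

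**The case against.** The strongest reply is that the plan already gives the DSMB ample means of seeing these events. P.3 has all adverse events reviewed by treatment arm. P.1 anticipates a comparison of adverse-event rates between arms at 6 months and then annually. Appendix 4 supplies serious adverse events by group with individual descriptions, and offers further safety analyses if the DSMB asks. Charter items 7 to 9 are general enough to take in any event. Table 3 itself has unfilled rows. All of this stands. It means that a DVT, infarction or stroke could be seen, and it limits the point to the absence of a pre-specified, named count.

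A reader might infer from Table 3 alone that transfusion reactions displaced the drug's known risks altogether. The documents do not support that: seizures and pulmonary embolism are defined outcomes, charter safety items and by-arm rows in Table 6. Which numbered table holds them is a matter of presentation.

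A reader might also expect the transfusion rows to be mostly empty or irrelevant. Section H.2 reports that over 65% of patients meeting these criteria in the applicants' own air medical data were transfused within 24 hours, so those rows may well fill. The documents do not say why they were chosen.

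Finally, C.8 is not one-sided. Besides calling the military result confounded, it reports no difference in deaths from vascular occlusive events (infarction, stroke and pulmonary embolism among them) in a randomised trial of over 20,000 patients, and no higher risk of venous thromboembolism in an orthopedic meta-analysis. This tempers the prior level of worry. But deaths do not speak to non-fatal events, elective joint surgery is a different population from trauma, and the protocol still lists thrombosis among the main complications.

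**Conclusion.** The point holds in a limited form. Table 3 specifies a set of rows that does not match the hazards C.8 names, and three thrombotic or vascular events (DVT, myocardial infarction and stroke) have no named by-arm row in Tables 3 to 6 and no named place on the charter list. Of these, DVT matters most, because C.8 cites an increase in it, albeit from a confounded comparison.

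This is an inexpensive improvement to safety reporting, not a flaw in the trial's inference. It does not show that thrombotic harm would go undetected, since the general routes remain open. The documents give no expected rate for any of the three events, so no count of potentially unlisted events can be drawn from them, and none is offered here. The conclusion rests on reading the table shells as the intended display. If the filler rows of Table 3 were already meant for these events, the remaining step is to say so.

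**What to change.** Add DVT, stroke and myocardial infarction to Table 3 as rows by arm; the three unlabelled rows already in the shell would hold them. Keep allergic/anaphylactic reaction. The transfusion rows may stay or go. Seizure and pulmonary embolism can be cross-referenced from Table 6 so that the drug-related hazards can be read in one place.

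Name the same three events on the charter's list of monitored adverse events. The charter provides for amendment by agreement of the principal investigator and the DSMB.

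Give each event a one-line definition, since I.4 has none. Basing it on a clinical diagnosis recorded in the adverse-event log or discharge summary uses sources already in the plan.

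The cost is more than a change of table wording: a short definition for each event, a coding step and three extra lines per report. The counts will depend on how readily each site looks for and diagnoses these events, so they should be read with that in mind. The per-centre columns help here. Sample size, alpha, power and treatment procedures are unchanged.
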